2. SUBJECT POPULATION AND ELIGIBILITY

Subject Population

- Subjects will be recruited from our ambulatory sports medicine clinics. We will include patients aged 18-60 who suffered a rotator cuff tear and are undergoing Rotator Cuff reconstruction.
- Subjects will be excluded if they are undergoing revision RCR reconstruction, history of DVT, neurovascular injury, unable to tolerate BFR treatment, unable to complete physical therapy and peripheral vascular disease

Enrollment and/or Screening

- Subjects will be identified when they present to our ambulatory clinics with RCR tears. We will not access the medical record prior to presentation to our clinics. At the presentation we will discuss the project with potential subjects and if they express interest, we will then delve further into the chart to ensure they do not meet any exclusion criteria. Additionally, we will discuss exclusion criteria with the patient during a detailed history. We will develop a series of questions to screen for exclusion criteria, particularly relating to the history or family history of DVT.

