3. STUDY PROCEDURES

- Patients who are seen in clinic for rotator cuff pathology will undergo treatment for their rotator cuff based

on a shared decision-making process with the orthopedic surgeon, irrespective of this study. Once a treatment plan is in place, the patient will be introduced to this study and presented with the opportunity to participate. If the patient agrees, a formal consent process will take place in clinic and the patient will undergo initial, baseline testing of strength, range of motion, pain scores, and patient reported outcome scores.

Therefore, patients will be either in the nonoperative arm or the operative arm of this study. Within each arm, patients will be randomized via computer to be placed in either the blood flow restriction (BFR) cohort or the traditional (non-BFR cohort). Patients will prospectively undergo rotator cuff rehabilitation using BFR or conventional therapy by physical therapists with extensive experience in rotator cuff rehabilitation who will undergo training on use of BFR.

The nonoperative group will be given identical rehabilitation protocols, with the only difference being the use of a BFR cuff during rehabilitation for the BFR cohort. Similarly, the operative group will be given identical rehabilitation protocols, with the only difference being the use of a BFR cuff during rehabilitation for the BFR cohort.

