Patients undergoing operative rotator cuff repair (RCR) will undergo preoperative rehabilitation prior to surgery for two weeks. Due to limitations of health insurance coverage of physical therapy sessions, the two weeks of preoperative "prehab" will consist of a structured home exercise program that is taught to the patient by a physical therapist during one session and recorded on a physical therapy (PT) diary by the patient during the two weeks leading up to surgery. Patients will be provided with video instruction and training on how to conduct the exercises and this will also be done with and without the use of BFR depending on group allocation (via randomization). Additionally, warning signs for BFR cuff intolerance such as increased pain, swelling, numbness/tingling of the arm will be communicated to the patient. Following surgery patients will immediately be started in a formal physical therapy regimen as an outpatient. Therapy will consist of a structured program progressing from range of motion to strength training and then functional tests. Patients will remain in their allocated BFR or non-BFR group.

Protocol as follows, both groups will use the same protocol with the only difference being use of BFR:

For surgical patients:

- Preop: Patients will undergo a home program consisting of isometric exercises including shoulder extension, abduction, external rotation and internal rotation pushing against a wall.

For both surgical and non-surgical patients:

- Post-op weeks 0-8: Passive shoulder range of motion (ROM) only
- Sling immobilization with active elbow, wrist and hand ROM
- Passive ROM only of shoulder including pendulums, supine elevation in scapular plane, external rotation with arm at side.

8-12 weeks being more active range of motion

- Discontinue sling
- Being active exercises including prone row, standing internal/external rotation with bands, wall slides into shoulder flexion

Weeks 12-20: Strength and function of Side lying shoulder external rotation, increase resistance band exercises

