Throughout this protocol patients will have a pre-operative visit, an early 2 week post operative visit to check range of motion and wound healing, a six week visit to monitor range of motion and potentially clear for active ROM and sling discontinuation, and a three month visit prior to clearance to being return to more aggressive activity. Strength and range of motion will be recorded at each of these visits in order to assess the primary endpoint.

Outcomes:

Primary Outcome:

- Strength to be measured via dynamometer at each clinic visit

Secondary Outcomes:

- Range of motion via goniometer
- Pain via visual analogue scale (VAS) pain scale at each visit
- Patient reported outcomes scores at each visit
- Fatty infiltration and muscle atrophy measured via ultrasound and compared to pre-operative imaging

Plan to recruit patients starting in June 2020. Will enroll patients and collect data from June-2020 to May 2021. Manuscript writing and submission to occur in June 2021.

Data analysis: The primary endpoint of this study was a maximum repetition total work deficit of 15% between the BFR and control group as measured by dynamometer. This was based on previous data showing that a strength deficit of 15% represents a clinically significant difference that is not likely attributable to limb dominance. Work deficit was calculated in each group by comparing the operative leg with the nonoperative leg to obtain a deficit percent. A power analysis was performed before the study to assess the number of patients needed to detect a 15% total work deficit between the BFR and control groups. With a power of 80% (beta level $\frac{1}{4} 0.80$, alpha level $\frac{1}{4} 0.05$), a sample size of 34 (17 patients per group) was obtained. Data will be provided to and analyzed by trained statisticians to determine differences in primary and secondary outcomes.

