All continuous data will be analyzed using independent 2-group t tests and reported as means \pm standard deviations. Categorical data will be compared between the 2 groups using chi-square tests and reported as counts and percentages. A preliminary test to confirm the quality of variances will be conducted prior to utilizing the t test to confirm the appropriate statistical analysis. Nonparametric equivalents Wilcoxon rank-sum and Fisher exact tests will be used as needed for nonnormal distributions and low variable numbers, respectively. A multivariable regression analysis was performed to assess potential confounding demographic variables.

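### The primary comparison is an unadjusted t test although baseline values are collected on every patient; ANCOVA on a pre-randomisation baseline gains power once its correlation with follow-up exceeds about 0.2

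*Combined protocol and SAP*

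**What the plan says.** All of this is in the combined protocol and SAP.

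- **Analysis.** The analysis text of section 3 says "All continuous data will be analyzed using independent 2-group t tests", with a rank-sum test as fallback. A multivariable regression is mentioned, but only for demographic confounders, and it is not the primary test.
- **Baseline.** Section 3 says that after consent "the patient will undergo initial, baseline testing of strength, range of motion, pain scores, and patient reported outcome scores". Randomisation is described next, so this testing appears to come first, though the text does not say so outright.
- **Allocation.** "Within each arm, patients will be randomized via computer" to BFR or conventional therapy, the arms being operative and non-operative. Section 2, however, admits only patients "who suffered a rotator cuff tear and are undergoing Rotator Cuff reconstruction".
- **Prehab.** Operative patients do a two-week home programme before surgery, and "this will also be done with and without the use of BFR depending on group allocation (via randomization").
- **Primary endpoint.** A between-limb total work deficit on the dynamometer: "Work deficit was calculated in each group by comparing the operative leg with the nonoperative leg to obtain a deficit percent". No baseline term appears in it, and no primary visit is named.
- **Size.** For 80% power at alpha 0.05 and a 15% difference, "a sample size of 34 (17 patients per group) was obtained". No SD is given, and the text does not say whether 34 is overall or per arm.

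**The concern.** In a trial this small, the patient's own starting value is often the cheapest source of precision. Here it is collected on everyone and then left out of the analysis. The between-limb deficit does not replace it: the other limb is a reference for the measurement, not an adjustment for how large that patient's deficit was at entry.

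Arm raises a second question. If the two arms are pooled, balanced within arm and differ at follow-up, that difference inflates the error term of the t test without affecting the treatment contrast. The test then rejects too rarely.

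At stake is the width of the interval and the chance of detecting a real effect. The randomised comparison is not biased by leaving covariates out. (Section 10 destroys withdrawn patients' data. That is a separate problem, which adjustment does not repair.)

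**Working it through.** **Inputs.** From section 3: 17 per group, power 80%, alpha 0.05, difference 15 points. Assumed because the plan is silent: two-sided test, no dropout, equal SD at baseline and follow-up, and a range for the baseline-to-follow-up correlation ρ.

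**1. The plan's own figure.** Without an SD, 17 per group cannot be reproduced, so I solved for the implied effect. The t test has 32 df and noncentrality d·√(17/2). Power of 80% gives d = 0.991, an implied SD of 15/0.991 = 15.1 points. This SD is illustrative only, since the endpoint is worded for legs.

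**2. Baseline adjustment.** ANCOVA with one covariate has 31 df and noncentrality d·√(34/4)·√(1−B)/√(1−ρ²). B is the chance imbalance in the covariate, distributed Beta(1/2, 16). Its mean cost in variance is E[1/(1−B)] = 31/30, so the variance breaks even when (1−ρ²)·31/30 = 1, i.e. ρ = √(1/31) = 0.18. On power, break-even is also 0.18, or 0.19 with a balanced arm term added. For a t test on change, d is replaced by d/√(2(1−ρ)). Simulation agrees with these results.

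| ρ (assumed) | t test on follow-up | ANCOVA | t test on change | ANCOVA 95% half-width (SD) |
|---|---|---|---|---|
| 0 | 80% | 79% | 51% | 0.705 |
| 0.2 | 80% | 80% | 60% | 0.691 |
| 0.3 | 80% | 82% | 66% | 0.673 |
| 0.5 | 80% | 89% | 80% | 0.611 |
| 0.7 | 80% | 97% | 95% | 0.504 |

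The half-width for the t test on follow-up values is 0.693 SD.

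**3. Dependence on sample size.** The threshold of about 0.2 belongs to one analysis of 34 patients. At 68 it is 0.13. With about 16 patients, as when 34 is split across two separately analysed arms, it is 0.28, and the loss at ρ = 0 is about 3 points.

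**4. Arm, only if pooled.** Assume 18 operative and 16 non-operative patients, and an arm gap at follow-up in within-arm SDs. With allocation balanced within arm, the residual sum of squares of the t test is noncentral chi-square with 32 df and noncentrality gap²·18·16/34. At a gap of 1.0 that is 8.47, so the expected error variance is (32 + 8.47)/32 = 1.26 times the within-arm variance.

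| Balanced within arm | gap 0.5 | gap 1.0 | gap 1.5 |
|---|---|---|---|
| t test, type I error | 4.3% | 2.8% | 1.4% |
| Power, planning SD is within-arm: t test / adjusted | 78 / 80% | 72 / 80% | 63 / 80% |
| Power, planning SD is total: t test / adjusted | 81 / 82% | 82 / 88% | 85 / 94% |

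With unblocked allocation the type I error stays at about 5%. t-test power is then 76, 69 and 59% against 77% adjusted (within-arm SD), or 79% throughout against 80, 86 and 93% adjusted (total SD).

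**5. Worst case with both covariates.** If neither is prognostic, power goes from 80.0 to 78.5% (balanced) or from 78.7 to 75.9% (unblocked).

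**6. Timing of the covariate.** If allocated prehab has already moved the covariate by a fraction f of the final effect, the adjusted estimate has expectation d(1 − ρf). At ρ = 0.5 and f = 0.10, 0.25 and 0.50 it shrinks by 5, 12.5 and 25%. Power falls from 89% to 86, 79 and 64%.

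**The case against.** The best defence is that nothing is broken. The t test is valid and, on the back-solved basis, reaches the 80% that was planned. The benefit of adjustment rests on a correlation the documents do not supply. For operative patients, surgery, a sling and weeks of passive motion lie between baseline and three months, so a high value cannot be presumed. At ρ = 0.3 the gain is only about 2 points. All of this stands, and it is why the point is a recommendation and not an error.

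Section 1 speaks of strength gains, and the ultrasound outcome is "Fatty infiltration and muscle atrophy measured via ultrasound and compared to pre-operative imaging", so change scores may be intended. The analysis text does not say so for the primary endpoint. A change score also does worse than the plain t test below ρ = 0.5. If the planning SD was that of change, ANCOVA still raises 80% to about 93, 89 and 85% at ρ = 0.3, 0.5 and 0.7; the gain is then largest at the low correlations.

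The arm argument is conditional. Pooling is nowhere stated, section 2 admits only reconstruction patients, and the visits and deficit definition in section 3 are operative. The shortfall below 80% under balanced allocation appears only if the planning SD was within-arm. That limit is accepted; the baseline argument does not depend on pooling.

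Finally, section 3 promises baseline strength, not explicitly the bilateral total work deficit. The covariate exists in the required form only if that test is done at entry.

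**Conclusion.** The point holds, as a recommended improvement in precision with medium confidence. An unadjusted t test is a weaker choice than ANCOVA on data the trial already plans to collect. In one analysis of 34 patients, adjustment for a pre-randomisation baseline breaks even at a correlation of about 0.2, gains about 2 points of power at 0.3, about 9 at 0.5 and about 17 at 0.7, and loses about 1.5 at zero. These sizes rest on the back-solved effect of 0.99 SD, equal SDs at the two times, a two-sided test and assumed correlations. The arm term matters only if both arms are enrolled and pooled. The gain is forfeited, and the estimate is pulled towards zero, if the covariate is measured after an effective prehab has begun.

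**What to change.** Make the primary analysis a linear model of the dynamometer work deficit at one named visit (for example three months, the last listed in section 3). Terms:

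- treatment group;
- the same measure taken before randomisation and before any allocated prehab;
- operative/non-operative arm if the arms are pooled. Omit it if the arms are analysed separately or only operative patients enrol.

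Use the same form for range of motion, VAS pain and patient-reported scores, and for ultrasound only where a comparable pre-randomisation value exists. State that no value taken after prehab starts is a covariate. Keep the t test as supportive. If a distribution-free fallback is wanted, rank ANCOVA or a permutation test of the adjusted treatment term (permuting within arm if pooled) fits this model better than the rank-sum test; this is optional.

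The text should also settle what the model depends on: whether the arms are pooled, whether 34 is overall or per arm, whether allocation is blocked within arm, which SD the sample size used, and the limb wording of the deficit.

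The cost is a short paragraph, one or two degrees of freedom, and confirmation that the entry test records the same bilateral measure before randomisation. At 34 patients the worst-case loss of power is about 1.5 points (blocked) to 3 points (unblocked).

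### BFR versus control is randomised within the operative and nonoperative arms, but no stated analysis includes arm, and the power statement (80%, 34 patients) does not say whether the comparison is pooled, per arm or operative-only.

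*Combined protocol and SAP*

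**What the plan says.** All references are to the combined protocol and SAP.

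- **Randomisation (Section 3).** Arm follows from shared decision-making and is not randomised. Then: "Within each arm, patients will be randomized via computer to be placed in either the blood flow restriction (BFR) cohort" or the traditional cohort. The operative arm alone has surgery and two weeks of prehabilitation.
- **Analysis (Section 3, after the outcomes list).** "All continuous data will be analyzed using independent 2-group t tests". "Categorical data will be compared between the 2 groups" by chi-square, with Wilcoxon rank-sum and Fisher exact tests as fallbacks. Also: "A multivariable regression analysis was performed to assess potential confounding demographic variables". Its covariates are not listed.
- **Power (Section 3, Data analysis).** For a 15% total work deficit between BFR and control, at 80% power and alpha 0.05, "a sample size of 34 (17 patients per group) was obtained". No SD, sidedness or arm is given.
- **Endpoint (same paragraph).** "Work deficit was calculated in each group by comparing the operative leg with the nonoperative leg to obtain a deficit percent".
- **Eligibility (Section 2).** Patients "who suffered a rotator cuff tear and are undergoing Rotator Cuff reconstruction".
- **Aim (Section 1).** The question is asked for both nonoperatively and operatively managed tears.

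**The concern.** The trial builds arm into its randomisation and then leaves it out of every analysis it states. Surgery and prehabilitation belong to one arm only, so the arms may well differ in mean strength deficit. In a pooled t test that difference goes into the error term, although the design allows it to be removed.

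The second part concerns the reach of the 80%. Section 1 asks the question for both arms, and a reader cannot tell whether 34 patients serve one pooled comparison, each arm, or operative patients alone. These are different trials: 34 in total, 68 in total (2 × 34), or 34 operative patients with the nonoperative arm outside the calculation.

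**Working it through.** **1. The plan's own figure.** The 34 cannot be reproduced, because no SD is given. Solving backwards with a difference of 15 points and n = 17 per group:

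- Power = P(|T| > t(0.975, df)), where T is noncentral t, df = n1 + n2 − 2 and noncentrality = (15/SD) × √(n1·n2/(n1 + n2)).
- Two-sided, 80% needs SD = 15.14: 15/15.14 = 0.991 and √(17·17/34) = 2.915, so noncentrality is 2.889 on 32 df. SDs from 14.65 to 15.14 all give exactly 17 per group.
- One-sided, the SD would be 17.21.

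The 34 is therefore neither confirmed nor refuted. What follows is an illustration at SD 15.14, two-sided.

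**2. What omitting arm does to a pooled test.** Assume 34 in total, cells of 8/8 in one arm and 9/9 in the other, and an arm mean difference D. Each treatment group then has 8 patients from one arm and 9 from the other.

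- The arms cancel in the BFR-minus-control difference, so its true sampling SD is still 15.14 × √(2/17).
- The t test's estimated variance is inflated. Its expectation is SD² + D² × (8·9/17)/16 = 229.1 + 0.2647·D².
- D = 10: 229.1 + 26.5 = 255.6, a working SD of 15.99. D = 20: 229.1 + 105.9 = 335.0, a working SD of 18.30.

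The standard error is thus too large. Power falls and the test is conservative. With an arm term, noncentrality is unchanged and df is 31, so power is 79.9% whatever D is.

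**3. Results.** The unadjusted figures are simulated, 200,000 or more trials per scenario; the D values are assumptions.

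| Two-sided, cells 8/8 + 9/9 | D = 0 | D = 10 | D = 20 |
|---|---|---|---|
| 15.1 as within-arm SD: unadjusted power | 80% | 77% | 66% |
| 15.1 as within-arm SD: arm-term power | 80% | 80% | 80% |
| 15.1 as within-arm SD: unadjusted type I error | 5% | about 3.8–3.9% | about 1.8–1.9% |
| 15.1 as overall SD: unadjusted power | 80% | 81% | 86% |
| 15.1 as overall SD: arm-term power | 80% | 84% | 96% |

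For the overall-SD rows, the within-arm SD is √(229.1 − D²/4): 14.29 at D = 10 and 11.36 at D = 20.

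**4. Chance imbalance.** With cells 9/8 + 8/9 or the mirror image, and 15.1 as the within-arm SD, unadjusted power is 73% or 80% at D = 10 and 58% or 74% at D = 20, depending on which way the extra patient falls. The arm-term model stays at 79.8%.

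**5. Simple randomisation within arms of 17.** Type I error is about 5% for both tests. Power (within-arm SD), unadjusted versus arm term: 74% versus 77% at D = 10, and 63% versus 77% at D = 20.

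**6. A single arm, if 34 is the total.** At within-arm SD 15.14:

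- 8 versus 8: noncentrality 0.991 × √4 = 1.982, power 45%.
- 9 versus 9: noncentrality 0.991 × √4.5 = 2.102, power 51%.

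**7. Sensitivity to the SD.** Pooled with an arm term, and one arm of 8 versus 9: 94% and 67% at SD 12; 56% and 30% at SD 20.

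**The case against.** **Pooling is not established.** Comparing two groups fits a separate test in each arm as well as a pooled one. The eligibility wording and the deficit defined by the operated limb point towards an operative-only calculation. On either of those readings an arm term has no role and the power loss disappears. This stands: a reader might infer that one pooled comparison of 34 is what the plan intends, but the documents do not settle it. The arm-term advice is therefore conditional, and the unstated scope is itself part of the point.

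**The planned test is not invalid.** A reader might infer that ignoring the randomisation strata inflates type I error. It does not: the test is conservative with balanced cells and holds about 5% with simple randomisation. If 15.1 is the overall SD, the unadjusted test in balanced cells even has 81% or 86% power, above the stated 80%. This also stands; the loss is of precision.

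**The t test is not the only analysis.** A reader might conclude that nothing but unadjusted t tests is planned. The section also lists chi-square, Wilcoxon, Fisher and a multivariable regression. But that regression is described as addressing demographic confounders, and arm is a treatment stratum, so the gap on arm remains.

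**The size rests on undocumented inputs.** True: the SD, its type, the arm difference, the arm split, blocking and sidedness are all absent. The gain could be near zero or substantial.

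**Conclusion.** The point holds as a should-fix matter. Two statements rest on the text alone: no stated analysis includes arm although randomisation is within arm, and the scope of the 34 and the 80% is not given.

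The loss of efficiency is conditional on a pooled comparison and on arms that differ. With balanced cells and two-sided testing, the arm term gains about 3 points of power at an assumed 10-point arm difference, and 10 to 13 points at 20. A one-patient imbalance widens this, on the within-arm reading, to about 0 to 7 and 6 to 22 points.

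It would go too far to call the sample size wrong or the trial underpowered. Without an SD the 34 cannot be tested, and the 45–51% for one arm matters only if 34 is the total and arm-specific conclusions are wanted.

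**What to change.** 1. **If the primary comparison is pooled over both arms,** replace the unadjusted t test with a linear model containing treatment and arm, arm being the stratification factor. Cost: one degree of freedom (31 instead of 32). If the arms do not differ, this loses about 0.1 point of power with balanced cells or about 1.4 points with simple randomisation. The term itself needs no added enrolment.
2. **State which comparison the 34 and the 80% cover.** If 34 is the total, limit the 80% to the pooled comparison, and report arm-specific effects and the BFR-by-arm interaction as estimates with 95% confidence intervals, without arm-specific efficacy claims. If 34 per arm was meant, say so and give 68. If operative-only was meant, say so and limit the 80% to those patients. Any power figure added should come from the sponsor's own SD, identified as within-arm or overall, and not from the illustration here.
3. **Before pooling,** reconcile the work-deficit definition in Section 3 and the eligibility statement in Section 2 with the nonoperative arm; neither fits it as written.

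Items 1 and 2 take one model term and a rewritten paragraph. Item 3 needs a decision by the sponsor on definition and population. Enrolment changes only if per-arm power was intended and 34 had been planned as the total.

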1. STUDY AIM, BACKGROUND, AND DESIGN ABSTRACT

The purpose of this study is to examine the effect of utilizing blood flow restriction (BFR) therapy in patients treated both non operatively and operatively for rotator cuff tears (RCT). BFR has been proposed to work by restricting arterial inflow leading to an oxygen depleted environment and the ability to induce muscle adaptation at lower maximum repetition via reactive hyperemia. Muscle atrophy occurs following rotator cuff tear. Thus, physical therapy is used to regain strength with the ultimate goal of returning to activity.

The goal of this investigation is to determine if using BFR during therapy for non-operatively managed and operatively managed rotator cuff tears would lead to increased and expedited strength gains. Additionally, the investigators would like to determine if BFR is beneficial in preventing muscle atrophy and fatty infiltration often seen in the setting of rotator cuff tear, as it is known that cuff tears can subject the muscles to degenerative changes and these patients are at risk for poorer clinical outcomes. The investigators will also look at patient reported outcomes metrics and pain scores to determine if BFR has a significant impact on the patient experience surrounding rotator cuff tear after both nonoperative treatment with therapy and operative treatment with surgical repair and peri-operative rehabilitation.

The investigators hypothesize that the BFR group will have significantly greater strength gains at all time points. Previous studies have shown that BFR has potential in increasing muscle torque generation and cross-sectional area in the first six months following anterior cruciate ligament (ACL) reconstruction. While there have not been as many studies investigating the use of BFR following upper extremity surgery, previous research has demonstrate that BFR can be useful both proximal and distal to the targeted muscle groups in the upper extremity. In addition to the paucity of research on post-operative BFR following rotator cuff repair (RCR), there is no evidence on pre-operative use as well. The investigators believe that the use of BFR in the perioperative period surrounding rotator cuff tear and repair has the potential to significantly decrease muscle atrophy and lead to faster, more substantial strength gains and less muscle atrophy and fatty infiltration.

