10. WITHDRAWAL OF SUBJECTS

- Subjects will be withdrawn from the study if they are unable to tolerate the BFR therapy. Additionally, if they suffer from any complications of the therapy they will be withdrawn immediately. This will be facilitated by describing the reasons for withdrawal to the patient prior to initiating the study and ask patients and other providers to inform the investigators if there are any issues or concerns.

- Data collection on patients who were withdrawn will be terminated and data destroyed.
- Patients may withdraw from the study at any time for any reason without affecting the quality of their care

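### Outcomes measured at four visits are compared only by two-group t tests, which waste baseline and earlier-visit data, do not estimate speed of gain, and can bias the BFR comparison if missed visits depend on earlier results differently by group.

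*Combined protocol and SAP*

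**What the plan says.** All references are to the combined protocol and SAP.

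- **Visits.** Section 3 (Study Procedures) sets baseline testing after consent, then a pre-operative visit and visits at 2 weeks, 6 weeks and three months. It states: "Strength and range of motion will be recorded at each of these visits in order to assess the primary endpoint". Pain is also taken at every visit, and the secondary outcomes include "Patient reported outcomes scores at each visit".
- **Analysis.** The same section says "All continuous data will be analyzed using independent 2-group t tests", summarised by means and standard deviations. The fallback is also cross-sectional: "Nonparametric equivalents Wilcoxon rank-sum and Fisher exact tests will be used as needed". The only model is described thus: "A multivariable regression analysis was performed to assess potential confounding demographic variables". No earlier outcome value and no visit term is named.
- **Aim.** Section 1 asks whether BFR "would lead to increased and expedited strength gains" and expects BFR to be superior at every time point.
- **Losses.** Section 10 says "Patients may withdraw from the study at any time for any reason". It also withdraws patients who cannot tolerate BFR or who have complications, and has the data of withdrawn patients destroyed. No analysis set, imputation rule or missed-visit rule is given.

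**The concern.** A two-group t test on multi-visit data, with no missing-data rule, amounts to a separate comparison of whoever was measured at each visit. Three consequences follow.

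1. **Precision.** Baseline and earlier follow-up values predict the later value but are not used. With 17 patients per group this matters.
2. **Question.** Whether gains come sooner is a question about how the group difference changes over visits. Separate cross-sectional tests do not estimate that.
3. **Possible bias.** A patient without a 3-month value drops out of that comparison even if the 6-week value shows how they were doing. Only BFR patients wear the cuff, section 4 expects some discomfort from it, and BFR intolerance as a ground for withdrawal can arise only in that group. It is therefore plausible, though not established, that the link between poor progress and missed visits differs by group.

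**Working it through.** **Scale of the design.** The plan gives a 15-point difference in work deficit, 80% power, alpha 0.05 and 17 per group, but no SD, so its sample size cannot be reproduced directly. Solving for the SD (two-sided test assumed), n per group = 2(1.960 + 0.842)² × (SD/15)² = 15.70 × (SD/15)². With SD 15.6 this is 15.70 × 1.0816 = 16.98, or 17. The t-based version gives 17 at SD 15.1. The trial is thus sized for d of about 15/15.6 = 0.96 to 15/15.1 = 0.99.

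**Precision.** With correlation ρ between baseline and outcome, baseline adjustment multiplies the variance of the group difference by 1 − ρ². Analysing change from baseline multiplies it by 2(1 − ρ).

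| ρ (assumed) | 1 − ρ² | 2(1 − ρ) |
|---|---|---|
| 0.7 | 0.51 | 0.60 |
| 0.5 | 0.75 | 1.00 |
| 0.7³ = 0.343 | 0.88 | 1.31 |
| 0.5³ = 0.125 | 0.98 | 1.75 |

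The last two rows apply if correlation falls by the same factor at each of three steps between visits. Adjustment gains from almost nothing to about half the variance, and is never worse than change scores. In simulations with 26-30 of 34 patients seen at 3 months, adjacent-visit correlation 0.5-0.7 and missingness unrelated to group, power at d = 1.0 was 70-77% for the t test and 71-82% for the repeated-measures estimate.

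**Bias.** The documents give no correlation or dropout rate, so these are assumptions. Suppose the chance p of missing 3 months rises with a worse 6-week value (logistic slope 1 per SD) in BFR only, and a fraction m is missing. The mean 6-week value of those seen shifts by E[p(1 − p)]/(1 − m) SD. The 3-month t test is then biased by ρ times that, where ρ is the 6-week to 3-month correlation.

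| m | E[p(1 − p)] (numerical integration) | shift | bias, ρ = 0.5 | bias, ρ = 0.7 |
|---|---|---|---|---|
| 12% | 0.0948 | 0.0948/0.88 = 0.108 | 0.054 SD | 0.075 SD |
| 20% | 0.1386 | 0.1386/0.80 = 0.173 | 0.087 SD | 0.121 SD |
| 25% | 0.1599 | 0.1599/0.75 = 0.213 | 0.107 SD | 0.149 SD |

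At 20% and SD 15.1 this is 1.31 and 1.83 points, against 1.31-1.83 points in a large simulation (400,000 per group). That simulation gave 0.63-0.98 points at 10% missing and 1.88-2.71 at 30%. An estimate using the earlier visits stayed within 0.07 points of the truth.

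Other mechanisms in the same simulation, at 10-30% missing:
- Opposite links in the two groups: 1.33-5.34 points towards BFR.
- The same rule in both groups, true effect 15 points: estimate 14.16-14.79, that is 0.21-0.84 points towards no effect.
- The same rule in both groups, no true effect: no bias beyond simulation noise.

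**At the trial's size.** In 4,000 simulated trials per scenario, with 17 per group, BFR-only linkage and no true effect, the t test was biased by 0.08-0.16 SD, with 5.5-7.0% false positives. A baseline-adjusted completers' test was biased by 0.07-0.12 SD. The repeated-measures estimate was within 0.012 SD of zero, with 3.9-4.6% false positives. A second set with 12-24% missing gave t test bias of 0.055-0.149 SD and false positives of 5.0-6.6%.

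**If withdrawn patients' records are deleted.** Their 6-week values no longer exist, and the repeated-measures estimate reduces to completers' ANCOVA. The bias is then 0.05-0.12 SD if correlation decays over visits and 0.02-0.06 SD if it is constant, against 0.05-0.15 SD for the t test.

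**The case against.** Much of the opposing case stands.

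- **The model would not rescue the losses most likely to differ by group.** A reader might infer that a mixed model removes bias from cuff intolerance. Under section 10 as written it cannot, because those patients' earlier visits are destroyed. It helps patients who miss a visit but remain in the study.
- **Bias is conditional.** A reader might infer that the t tests necessarily favour BFR. The documents do not show that. The direction depends on an assumed group-specific link, and a common rule gives no bias or a slight pull towards no effect.
- **The amount is small.** With 13-15 patients per group seen, the standard error is √(2/13) = 0.39 to √(2/15) = 0.37 SD, so 0.08-0.16 SD is about 0.2-0.4 of a standard error. A false-positive rate of 5.5% is within 1.5 Monte Carlo standard errors of 5% (√(0.05 × 0.95/4,000) = 0.34 percentage points). Serious error inflation is not supported.
- **Strength may gain little.** Section 3 limits the shoulder to passive motion in weeks 0-8, so strength values at 2 and 6 weeks are doubtful. If only one follow-up strength value is valid, no model can say whether strength returned sooner.
- **Baseline may be meant to enter through change scores**, since section 1 speaks of gains. The analysis text does not say so, and change scores would still ignore intermediate visits.
- **The simulated estimator** was a factored-likelihood one, so its error rates do not validate REML with Kenward-Roger at this size.

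None of this restores what the t tests leave out: baseline, earlier visits and the group-by-visit effect.

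**Conclusion.** The point holds as a matter of efficiency and of fit to the aim, with a conditional risk of bias. Without any dropout assumption, the plan discards baseline and earlier-visit information and does not estimate the change in group difference over visits. With group-specific, outcome-linked missed visits, the t test can be biased by about 0.05-0.16 SD towards BFR, or 0.8-2.4 points at SD 15.1 (0.05 × 15.1 and 0.16 × 15.1), against a 15-point target. This rests on assumed missingness of 12-25% in the BFR group and correlations of 0.5-0.7. The change should be made because it is cheap and uses data already planned, not because the t tests are shown to invalidate the trial. For strength, the benefit may be limited to baseline adjustment. The fuller gain is for range of motion, pain and patient-reported scores.

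**What to change.** 1. For each repeated continuous outcome, specify one linear mixed model with group, visit, group-by-visit, baseline, baseline-by-visit and operative/nonoperative arm (randomisation is within arm). Use unstructured covariance with a named simpler fallback for non-convergence, REML and Kenward-Roger degrees of freedom. Include every randomised patient with at least one follow-up value.
2. Define baseline as the value from testing at consent, because operative patients in the BFR group already use the cuff during the two preoperative weeks.
3. Name a primary visit. Report the group difference there as the main result and the group-by-visit estimates as the answer on speed.
4. If strength is valid at only one follow-up visit, use baseline-adjusted ANCOVA for it and do not claim to have assessed speed of strength gain.
5. Amend section 10 so that data already collected from withdrawn patients are kept, as consent permits. Without this, the model cannot use those patients' earlier visits.
6. Add a simple sensitivity analysis for departures from missing at random, for example shifting the unobserved BFR values by a stated range.

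Cost: SAP wording, slightly more analysis work and a few more parameters with 34 patients. No new visits or measurements are needed. Item 5 goes beyond SAP wording: it changes the protocol's data rule and may affect the consent text.
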